- Individual subject success criteria defined as a 30% or greater reduction in self-reported Degree of Pain rating on the 0-100 VAS from baseline to study endpoint evaluation.

N.B.: The clinical relevance of a 30% change in VAS score is explained and supported in the STATISTICAL ANALYSIS PLAN section further along in this protocol document.

- Overall study success criteria of at least a 35% difference between the active device group and the placebo device group, comparing the proportion of individual successes in each group.
- It is anticipated that about 55% of subjects in the active device group and about 20% of subjects in the placebo device group will meet the individual success criteria, and
- intended application of a two-tailed test with an alpha value of 0.05 and Power of 0.8

...the sample size of 29 subjects per group (active group and placebo group, separately) has been determined using the following reference calculator: *Hypothesis Testing: Categorical Data - Estimation of Sample Size and Power for Comparing Two Binomial Proportions* in Bernard Rosner's *Fundamentals of Biostatistics*.

For the purposes of sample size calculation, it is anticipated that about one-twentieth of subjects overall may withdraw from the study prior to completion for various reasons. Therefore, the following formula is used to determine the final needed starting sample size for each group:

Final sample size = sample size X 1/(1-d); where d = # expected dropouts/# subjects enrolled.

Final sample size = 29 X 1/(1-0.083)

Final sample size = 29 X 1/0.917 = 29 X 1.0905 = 31.62, rounded to 32 subjects per treatment group.

Therefore, a minimum starting sample size of 32 subjects in each treatment group is needed to ensure that sufficient numbers remains at the end of the trial (29 subjects per group) for any significant differences found between groups to be considered statistically valid and representative of the general population being sampled. This results in a total of 64 subjects being enrolled in this study across both study treatment groups.

STUDY PROCEDURE

STUDY TEST BATTERY

The following are the study assessment tools to be used and the variables to be recorded in this clinical study.

BASELINE VARIABLES

A. Neuropathy Variables

- Number of months/years since onset of foot pain.
- Number of months/years since diabetes diagnosis
- Insulin dependency

B. Medication and Treatment

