10 DAY EVALUATION

Following 10 days of study treatment administrations (20 treatment administrations) with the Erchonia® EVRL (approximately halfway through the treatment administration phase), the following will be recorded on the provided case report forms by the subject at home.

- Visual Analog Pain Scale (VAS) Degree of Foot Pain Rating

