Records for each subject in this clinical study will be maintained in separate files in a locked filing cabinet at the respective test site. The investigator at the test site will be responsible for ensuring that all records for a subject pertaining to his or her participation in the clinical study are maintained in the subject's file at all times other than when information is being recorded on them.

Copies of all subject case report forms will be made and supplied to the study statistician and Erchonia Corporation who will each maintain these copies in a separate clinical study file that is kept in a locked filing cabinet on their respective premises. The original records will be maintained at the respective test sites.

Subjects' identities will be kept confidential by assigning each subject a unique de-identified subject ID upon acceptance into the study. The subject ID will comprise the investigator's two initials (first and last name initials) and a three-digit number that will be based upon the subject's order of entry into the clinical study. For example, under Study Investigator John Black, the third subject enrolled in the study would have a subject ID of JB003.

MONITORING OF THE CLINICAL STUDY

A Clinical Trial Monitoring Plan will be in place to ensure on-going compliance and accuracy of procedures throughout the trial.

STATISTICAL ANALYSIS

STUDY ANALYSIS POPULATIONS

(i) Intent-to-Treat (ITT) Population

The Intent-to-Treat (ITT) analysis population is defined as all consented and enrolled subjects. The ITT population will comprise the principal population analysis for evaluation of study primary efficacy outcome.

(ii) Per Protocol Population

The per protocol analysis population is defined as all consented and enrolled subjects who completed the entire clinical study per protocol, inclusive of all treatment administrations and all study activities and assessments per protocol without missing data or major protocol deviations. The per protocol population will comprise the secondary population analysis of the study primary efficacy outcome to provide support for the principal ITT population analysis as well as for all secondary outcome assessments.

HANDLING OF MISSING DATA

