Based on over twenty-five (25) years of experience conducting comparable clinical trials through the study Sponsor, Erchonia Corporation, the relatively small sample size, the short duration of the trial, and the minimal requirements and commitments required from enrolled subjects, it is anticipated that withdrawal and lost-to-follow-up rates will be minimal and so will be missing data. Therefore, the single imputation methodology is selected as that to be implemented to account for any missing data. Single imputation methodology is applicable to impute missing values when a dataset is small, the number of missing values is small, the missing data is assumed to be Missing Completely at Random (MCAR), and outcome analysis procedures are simple. The single imputation methodology selected for this study is whichever is more conservative of the mean or the median of the variable for the treatment group from which the missing data emanated.

BASELINE RECORDINGS

SAMPLE DEMOGRAPHICS

Sample demographics recorded at Baseline assessment will be summarized descriptively by treatment group, using mean, standard deviation, median and range (minimum, maximum) for the continuous variable of subject age in years, and by number (N) and percentage (%) for the categorical sample variables of gender and ethnicity. Sample demographics will be compared for differences between treatment groups and test sites. Any identified differences will be explored with respect to potential impact on study outcome.

NEUROPATHY VARIABLES

Sample neuropathy continuous variables recorded at Baseline assessment of months since diagnosis of diabetes, and months since onset of peripheral neuropathy foot pain will be summarized descriptively by treatment group, using mean, standard deviation, median and range (minimum, maximum). The categorical Baseline neuropathy variable of presence or absence of insulin dependency will be summarized descriptively by number (N) and percentage (%) per category. Sample demographics will be compared for differences between treatment groups and test sites. Any identified differences will be explored with respect to potential impact on study outcome.

MEDICATION AND TREATMENT

The below medication and treatment usage as recorded at Baseline assessment will be summarized categorically by, and compared between, treatment groups using number (N) and percentage (%):

- (i) Current medications taken for relief of diabetic foot pain

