- (ii) Prior treatment approaches for relief of diabetic foot pain
- (iii) Concomitant medication and therapy use: non-pain relief indications

PRIMARY EFFICACY OUTCOME MEASURE: CHANGE IN SUBJECT SELF-REPORTED VAS PAIN RATING FROM BASELINE TO STUDY ENDPOINT

Primary efficacy outcome measure for this clinical study will be a statistically significant difference in the proportion of subjects between active and placebo treatment groups who achieve a clinically meaningful and statistically significant decrease in self-reported VAS pain rating from Baseline (pre-treatment) to study Endpoint (Week 3).

The principal primary efficacy outcome evaluation will be performed for the study intent-to-treat (ITT) population according to the following pre-determined primary efficacy success criteria.

Individual Subject Success Criteria

Individual subject success criteria is defined as a 30% or greater decrease ($\geq 30\%$) in self-reported pain rating on the 0 to 100 Visual Analog Scale (VAS) at study Endpoint (Week 3) relative to Baseline.

Overall Study Success Criteria.

Overall study success criteria defined as at least a 35% difference between treatment groups, comparing the proportion of individual successes in each group. It is anticipated that about 55% of subjects in the active treatment group will meet the individual success criteria and about 20% of subjects in the placebo treatment group will meet the individual success criteria.

The clinical relevance of a 30% change in VAS score has been well established by FDA's Division of Physical Medicine and Rehabilitation Devices. The following Erchonia Corporation light therapy devices (Product Code NHN) obtained FDA 510(k) clearance based on clinical trials employing the 30% VAS change as the primary efficacy endpoint for pain reduction:

1. K221987; 09/01/22: "Erchonia® GVL: is indicated while using the green and violet diode simultaneously, for adjunctive use in providing temporary relief of minor chronic neck and shoulder pain of musculoskeletal origin."
2. K191257; 08/08/19: "Erchonia® EVRL: is indicated while using the red and violet diode simultaneously, for adjunctive use in providing temporary relief of minor chronic neck and shoulder pain of musculoskeletal origin."
2. K180197; 5/21/18; "Erchonia® FX-635: is indicated for the following two indications:
 - a. as an adjunct to provide relief of minor chronic low back pain of musculoskeletal origin.

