 - b. as an adjunct to reducing chronic heel pain arising from plantar fasciitis."
3. K132940; 04/14/14: "The Erchonia Allay laser is indicated as an adjunct to reducing chronic heel pain arising from plantar fasciitis."

4. K012580; 01/17/02: "The TUCO Erchonia PL2000 is indicated for adjunctive use in providing temporary relief of minor chronic neck and shoulder pain of musculoskeletal origin."

Evaluation Time Point

The study end evaluation time point at which primary study success will be analyzed is at three weeks post-baseline, following completion of the 42nd and final study treatment administration with the Erchonia® EVRL.

Hypotheses

The pre-established null and alternative hypotheses for the primary efficacy outcome evaluation were the following:

(i) *Null Hypothesis:* The difference in the proportion of individual subject successes between the active and placebo treatment groups will be less than 35%.

$$H_0: \mu_A - \mu_P < 35\%$$

Where 'A' = active treatment group; and 'P' = placebo treatment group

(ii) *Alternative Hypothesis:* The difference in the proportion of individual successes between the active and placebo treatment groups will be 35% or greater in favor of the active treatment group.

$$H_1: \mu_A - \mu_P \geq 35\%$$

Where 'A' = active treatment group; and 'P' = placebo treatment group

(i) Responder Rate Analysis

Principal determination of study primary outcome success as defined will be according to Responder Rate Analysis calculated by determining the percentage of individual subject successes in each of the active and placebo treatment groups, separately, and then subtracting the two proportions to attain the difference in proportions between the two treatment groups. Overall Study Success will be demonstrated if this difference is $\geq 35\%$ in favor of the higher proportion occurring for the active treatment group.

(ii) Chi-Squared Analysis of Proportions

A chi-squared analysis to assess the significance of the difference in the proportion of individual subject successes (Responder Rate) between the active and placebo treatment groups will be performed. A two-tailed significance level of 5% will be considered statistically significant.

(iii) ANCOVA of Mean Change in Diabetic Peripheral Neuropathy Foot Pain VAS Ratings

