Parametric Analysis of Covariance (ANCOVA) with the mean change from Baseline to study Endpoint (Week 3) in diabetic peripheral neuropathy foot pain ratings on the 0-100 VAS as the dependent variable, treatment group as the independent variable of interest, and Baseline diabetic peripheral foot pain VAS rating as a covariate will be performed. A two-tailed significance level of 5% was predetermined to be considered statistically significant.

SECONDARY EFFICACY OUTCOMES

The following secondary efficacy outcomes will be evaluated to provide support for the primary efficacy outcome analysis. **As no claims are intended to be made based on the secondary efficacy outcome evaluations, secondary efficacy outcome analysis will be performed for the per protocol analysis population only and statistical analyses will not be performed; secondary efficacy outcomes data will be presented descriptively only.**

(i) Diabetic Peripheral Neuropathy Foot Pain VAS Ratings Across Study Progression

Descriptives of mean, standard deviation (SD), median, and range (minimum, maximum) will be presented in a table for the degree of pain ratings recorded on the 0-100 VAS for diabetic peripheral neuropathy pain at each of the four (4) study assessments of Baseline (pre-treatment), Day 10 (Post-Baseline), Endpoint (3 Weeks Post-Baseline), and Follow-Up (7 Weeks Post-Baseline - 4 Weeks Post-Treatment End) by treatment group.

(ii) Neuropathic Pain Symptom Inventory (NPSI) Scores Across Study Progression

Descriptives of the mean, standard deviation (SD), median and range (minimum, maximum) for each of the five (5) dimension scores on the NPSI and the Total NPSI score will be presented in a table for each of the three study assessments of Baseline, Endpoint (Week 3), and Follow-Up (Week 7) by treatment group.

SATISFACTION WITH STUDY OUTCOME RATINGS

Subject satisfaction scores will be presented descriptively in a table as number (N) and percentage (%) per response category (Very Satisfied, Somewhat Satisfied, Neither Satisfied nor Dissatisfied, Not Very Satisfied, Not at All Satisfied) at each assessment of Study Endpoint (Week 3) and Study Follow-Up (Week 7) by treatment group.

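### Filling missing Week 3 VAS with the own-arm mean or median of an undefined variable can tilt the 35-point primary result towards the device, and no missing-data sensitivity analysis is planned

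*Combined protocol and SAP*

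**What the plan says.** All references are to the combined protocol and SAP.

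- **Population** (Study Analysis Populations): "The ITT population will comprise the principal population analysis for evaluation of study primary efficacy outcome".
- **Endpoint** (Individual Subject Success Criteria): "Individual subject success criteria is defined as a 30% or greater decrease" in VAS at Week 3 relative to baseline.
- **Decision** (Responder Rate Analysis): "Overall Study Success will be demonstrated if this difference is" 35 percentage points or more in favour of active. A chi-squared test of the responder rates and a baseline-adjusted ANCOVA of VAS change follow, each at two-sided 5%.
- **Missing values** (Handling of Missing Data): single imputation with "whichever is more conservative of the mean or the median of the variable for the treatment group from which the missing data emanated". Part of the justification is that "the missing data is assumed to be Missing Completely at Random (MCAR), and outcome analysis procedures are simple".
- **Expected loss** (Rationale for sample size): the text says that "it is anticipated that about one-twentieth of subjects overall may withdraw from the study prior to completion for various reasons", but the formula uses 0.083 and goes from 29 to 32 per arm.

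The only other analysis of the primary outcome by population is per protocol. It is limited to subjects with every treatment and assessment, no missing data and no major deviation.

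**The concern.** A group centre is a poor stand-in for a yes/no outcome. The rule could be applied to Week 3 VAS, absolute change, percent change or responder status, and these give different results. The plan also does not say whether conservative means against the device in each arm or less improvement in both.

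If VAS, change or percent change is filled in, all dropouts in an arm receive the same centre. In the placebo arm that centre lies below the 30% cut-off, so nearly all become non-responders although a fifth should respond. In the active arm the centre lies near the cut-off, so dropouts tend to switch together.

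Success is a hard cut on a point estimate, so a shift of one subject can decide the trial. The filled values also enter the chi-squared test and the ANCOVA as if they had been observed.

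**Working it through.** **1. The plan's own figures.** Inputs from Rationale for sample size: 55% and 20% responders, two-sided 5%, power 0.80. With the pooled rate 0.375,

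n = [1.960·√(2·0.375·0.625) + 0.842·√(0.55·0.45 + 0.20·0.80)]² / 0.35² = (1.342 + 0.537)² / 0.1225 = 28.8, so 29 per arm.

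29/0.917 = 31.62, so 32. Both figures reproduce. The allowance is therefore 3 missing per arm; one-twentieth of 32 is 1.6, nearest to 2.

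**2. Step size.** One subject is 1/32 = 3.1 points. A net 11 responders gives 34.4 (fail) and a net 12 gives 37.5 (pass).

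**3. Where the centres lie.** With 80% of placebo subjects below the cut-off, the placebo median must be below it. For normal percent change the placebo mean is 0.842 SD below; over 29 subjects that is 0.842·√29 = 4.5 standard errors, so it almost never crosses. The active mean is 0.126 SD above, or 0.126·√29 = 0.68 standard errors. It therefore lands above the cut-off about 75% of the time. Taking the less favourable of mean and median lowers this to about 65% in simulation.

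**4. Expected difference with 3 missing per arm.** Let a and b be the fractions of imputed active and placebo dropouts counted as responders. Then

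D = 35·(29/32) + 100·(3/32)·(a − b) = 31.7 + 9.375·(a − b) points.

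The rule is neutral only if a − b = 0.35. With b = 0: a = 0.65 gives 37.8, a = 0.71 gives 38.4 and a = 0.31 gives 34.6.

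**5. Simulation.** Assumptions, none of them in the documents:
- baseline VAS N(70, 12) limited to 50–100;
- percent change normal or gamma-skewed (shape 2), SD 25–45, placed to give 55% and 20% responders;
- Week 3 VAS limited to 0–100;
- conservative read as less improvement for active and more for placebo.

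There were 40,000 trials per scenario. Ranges run over imputing VAS, change or percent change unless stated otherwise.

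| Missing per arm | Percent change | Expected difference | P(difference ≥ 35) |
|---|---|---|---|
| 0 | any | 35 | 0.47–0.48 |
| 1 | normal or right-skewed | 35.6–36.3 | |
| 1 | left-skewed | 34.9–35.2 | |
| 2 | normal | 35.9–37.0 | |
| 2 | right-skewed | 36.4–37.3 | |
| 2 | left-skewed | 34.9–35.5 | |
| 3 | normal | 36.3–37.8 | 0.52–0.59 |
| 3 | right-skewed | 37.0–38.4 | 0.54–0.61 |
| 3 | left-skewed | 34.6–35.7 | 0.44–0.49 |
| 3, non-responders twice as likely missing (SD 35) | normal or right-skewed | 37.9–39.4 | 0.57–0.65 |
| 3, same | left-skewed | 36.2–36.5 | 0.49–0.51 |
| 3, responder status imputed against the device | | 33.7–33.9 | 0.45 |

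With 3 missing, imputed placebo dropouts were responders 0–11% of the time (true 20%). Imputed active dropouts were responders 56–66% (normal), 64–71% (right-skewed) or 31–44% (left-skewed) of the time (true 55%). A separate run with normal data and other spreads of baseline VAS gave shifts of +0.65 to +2.9 points with 3 missing.

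Compared with completers only (3 missing, SD 35), the rule turned a fail into a pass in 8.8–16.0% of trials and a pass into a fail in 0.8–2.2% (normal or right-skewed). For left-skewed data these were 4.5–5.6% and 3.1–7.1%.

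**6. Worked example.** Completers 16/29 vs 6/29 differ by 10/29 = 34.5 points (fail). If two of three active dropouts and no placebo dropouts are imputed as responders, 18/32 vs 6/32 = 37.5 (pass). If all three are, 19/32 vs 6/32 = 40.6.

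**7. Tests with no true effect.** The ANCOVA two-sided error is 6.5–7.0% with 2 missing per arm and 7.7–8.1% with 3 (complete cases 4.8–5.2%). Its model standard error is about 7% and 10% too small. The chi-squared error at equal 20% rates is 4.9–5.7%.

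**The case against.** - **The shift is neither universal nor one-directional.** It is about nil for left-skewed change and goes against the device if responder status is imputed against it. This stands: the 1–3 points applies to normal or right-skewed data with about 2–3 missing per arm.
- **Week 3 VAS is the most natural reading of the variable.** On that reading, 2 missing per arm gives +0.9 to +1.5 points (normal), +1.4 to +2.0 (right-skewed) or −0.3 to +0.4 (left-skewed). This also stands, but the plan does not fix that reading.
- **The plan expects minimal missing data.** Its own sample-size allowance is nevertheless about 2–3 per arm. With 1 missing the average effect is well below one subject.
- **An ineffective device is not materially more likely to pass.** With no true effect, the 35-point rule is met with probability about 0.0001 at equal 20% rates and at most about 0.011 at equal rates of 40–55%. This stands. The harm arises when the true difference is near 35. Chi-squared error does reach 9–19% at equal rates of 40–55%, but those rates are far from the planned placebo rate and full data already give 5.5–6.0% there. The ANCOVA does not decide the trial.
- **The per protocol analysis contains no imputed values, and individual VAS values will be tabulated.** True, but per protocol also drops deviators, so it cannot isolate the effect of imputation. A table from which a reader could recompute is not a planned analysis.

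**Conclusion.** The point holds and should be fixed. That the rule is undefined and untested by any sensitivity analysis follows directly from the text. That placebo dropouts become non-responders too often follows from the planned 20% rate whenever VAS, change or percent change is imputed.

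The size depends on assumed distributions. Under data missing completely at random, with 3 missing per arm, it is +1.3 to +3.4 points for normal or right-skewed percent change at the main settings, and −0.4 to +0.7 for left-skewed change. It is larger if non-responders leave more often. Which case applies cannot be known in advance. The plan's own missingness assumption does not remove the tilt, because the tilt arises under it. The ANCOVA p-value is too small in every case simulated.

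**What to change.** Remove the mean/median rule and write into the SAP:

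1. **Primary handling.** Multiple imputation of Week 3 VAS within each arm from baseline and Day 10 VAS (the 10 Day Evaluation already records the "Visual Analog Pain Scale (VAS) Degree of Foot Pain Rating"). Limit values to 0–100 and state the seed and the number of imputations (e.g. 50). Impute Day 10 in the same run for subjects who leave before it.
2. **Order and pooling.** Derive responder status after imputation, and pool the responder difference and the ANCOVA with Rubin's rules. State that the pooled difference is compared with 35 points.
3. **Sensitivity analyses.** (a) Missing counts as non-response in both arms; (b) a tipping-point table over every split of imputed responders by arm.
4. **Consistency.** Reconcile the one-twentieth in words with the 0.083 in the formula.

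The cost is SAP wording and a little programming, with no new data. Multiple imputation gave 34.7–35.1 points under data missing completely at random (P of passing 0.49–0.51), and 35.2–35.7 with non-responders twice as likely to be missing. Those runs assumed that Day 10 was always observed and correlated 0.6 with Week 3, so they are somewhat favourable. The sponsor may prefer (a) as the simpler primary analysis, but it lowers the expected difference to 35·29/32 = 31.7 points with 3 missing per arm (P 0.35).

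### The success threshold equals the assumed effect, so the chance of success is about 47%, not 80%, and no planned test addresses the stated null hypothesis

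*Combined protocol and SAP*

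**What the plan says.** Three parts of the combined protocol and SAP bear on this.

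- **Rationale for sample size.** The inputs are "Overall study success criteria of at least a 35% difference between the active device group and the placebo device group", the expectation that "It is anticipated that about 55% of subjects in the active device group and about 20% of subjects in the placebo device group" will be responders, and "intended application of a two-tailed test with an alpha value of 0.05 and Power of 0.8". From these, "the sample size of 29 subjects per group (active group and placebo group, separately) has been determined"; this is then raised to 32 per group for dropout.
- **Primary Efficacy Outcome Measure.** The primary outcome is introduced as a statistically significant difference in responder proportions. It is then evaluated in the ITT population by the 35% criterion, and the 55% and 20% assumptions are repeated.
- **Hypotheses and the analyses that follow.** The null is that "The difference in the proportion of individual subject successes between the active and placebo treatment groups will be less than 35" percent; the alternative is 35% or more in favour of active. The plan then says "Principal determination of study primary outcome success as defined will be according to Responder Rate Analysis": subtract the two observed proportions and declare success if the result is at least 35%. A two-tailed 5% chi-squared test of the proportions follows, with no 35-point margin in it.

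**The concern.** The bar that the observed difference must clear is the same number as the true difference the sponsor expects. An estimate falls below its true value about half the time, so a rule of this form cannot have 80% power at the planning assumptions. The stated power must therefore belong to some other test.

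The hypotheses raise a second problem. A standard chi-squared test of two proportions asks whether they are equal. It does not ask whether their difference is below 35 points. The comparison that does use 35 points is a bare point estimate with no allowance for sampling error.

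At stake is the interpretation of the primary result. A device that performs exactly as expected could fail by rule while showing a clearly significant benefit. If success is declared, the stated null will not have been rejected at the 5% level.

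**Working it through.** **Inputs.** Active rate 0.55, placebo rate 0.20, two-sided alpha 0.05, power 0.80, 29 evaluable and 32 enrolled per group (Rationale for sample size); success if the observed difference is at least 0.35 (Responder Rate Analysis).

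**1. Reproduce the plan's figure.** The pooled two-proportion formula for a null of zero difference, with mean rate (0.55 + 0.20)/2 = 0.375, is

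n = [1.960 × √(2 × 0.375 × 0.625) + 0.842 × √(0.55 × 0.45 + 0.20 × 0.80)]² / 0.35²

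n = [1.960 × 0.6847 + 0.842 × 0.6384]² / 0.1225 = 28.83, so 29.

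This matches. The inflation 29/0.917 = 31.62, so 32, also matches. The 80% is therefore the power of a test of equality.

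**2. What the rule requires.** With 32 per group, 11/32 = 34.4% misses and 12/32 = 37.5% passes, so active needs 12 more responders than placebo. With 29 per group, 11 more are needed (37.9%).

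**3. Probability of success at 55% vs 20%.** This sums the two independent binomial distributions over all outcomes that meet each condition. The chi-squared test is uncorrected and counted only when it favours active.

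| Per group | Observed difference ≥35 points | Chi-squared significant | Significant but rule missed |
|---|---|---|---|
| 29 | 46.5% | 79.6% | 33.1% |
| 30 | 50.6% | 81.6% | 31.0% |
| 31 | 54.5% | 83.4% | 29.0% |
| 32 | 47.2% | 85.2% | 37.9% |

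At all four sizes every outcome that meets the 35-point rule is also significant (the smallest chi-squared at 32 per group is 9.0). Requiring both conditions therefore leaves the first column unchanged.

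**4. Effect needed for 80%.** With 32 per group and 20% placebo response, the rule is met with probability 79.7% at a true difference of 45 points and 82.2% at 46. The true difference must be just over 45 points.

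**5. The chi-squared test against the stated null.** With 6/32 placebo responders, 14/32 active is a 25-point difference: chi-squared = 0.25² / (0.3125 × 0.6875 × 2/32) = 4.65, p = 0.03. This rejects equality although the observed difference lies inside the stated null. With 17/32 active, the difference is 34.4 points and p = 0.004, yet the trial fails its own criterion.

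**6. The point-estimate rule against the stated null.** At 54.5% vs 20% (34.5 points) the stated null is true, and the rule declares success 45.5% of the time with 32 per group. A 5% test would not do this.

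**The case against.** Four points can be made for the plan.

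- **The 0.8 is right for the test it names.** The sample-size section ties it to a two-tailed 5% test, and the primary outcome is introduced as a statistically significant difference. This is true, and it means the plan carries two criteria and sizes the trial for one. It does not rescue the stated power, because the plan makes the 35-point comparison the principal determination and lists it among the sample-size inputs.
- **The rule is strict, not lax.** With equal true rates and 32 per group, it declares success at most about 0.2% of the time. This stands. The 45.5% in step 6 is an error rate against the stated null only; it is not a risk of passing an ineffective device.
- **47% depends on exact group sizes.** This also stands. Over arms of 29 to 33, equal or not, the probability runs from 46.5% to 54.5%. That failure is more likely than success holds at 29 or 32 per group; over the wider range it is about a coin toss. No size in that range comes near 80%.
- **A demanding threshold may be deliberate.** A sponsor may choose one, and the revision log says the plan was changed after a regulatory pre-submission whose content is not in the documents. That is a reason to keep the rule and disclose its properties, not to leave the power and hypotheses as written.

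**Conclusion.** The concern holds. The success rule, the stated power and the hypotheses for the primary endpoint do not fit together. At the plan's own assumptions (55% vs 20%, equal groups, independent binomial outcomes) the probability of declared success is 47.2% with 32 per group and 46.5% with 29, against a stated 80%. With 32 per group, about 38% of trials would end with a significant benefit and a declared failure. Neither the chi-squared test nor the point-estimate rule is a 5% test of a difference below 35 points. The harm is a low chance of success and a null hypothesis that is never properly tested; false success when the device has no effect is not inflated. The calculation leaves out the effect of imputing missing endpoint values.

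**What to change.** Choose one of two changes and fix it before unblinding.

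1. **Align the hypotheses with the planned test.** State the null as no difference in responder proportions and the alternative as a difference, tested by the two-sided 5% chi-squared test in the ITT population. Report the difference with a 95% confidence interval, and keep 35 points as the planning assumption or clinical benchmark. The sample size already supports this.
2. **Keep the 35-point rule as the success criterion.** State that its probability of success is about 47% at 55% vs 20% with 32 per group, attribute the 0.8 to the test of equality only, and describe the rule as a point-estimate criterion. Remove the claim that it tests a difference below 35%.

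Both need edits only to the hypotheses, success-criterion and sample-size paragraphs, and no added subjects. The first lowers the bar for success (with 6/32 placebo responders, from 18/32 active to 14/32), so it may need discussion with the regulator. The second leaves the bar alone but makes the stated power less favourable.
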